## 5.3. Lifestyle Considerations

Potential participants must be willing and able to adhere to the following lifestyle restrictions during the course of the study to be eligible for participation:

1. Refer to Section 6.5, Concomitant Therapy for details regarding prohibited and restricted therapy during the study.

2. Agree to follow all requirements that must be met during the study as noted in the Inclusion and Exclusion Criteria (e.g., contraceptive requirements).

## 5.3.1. Meals and Dietary Restrictions

- 1. Participants may not consume any food or beverages containing, grapefruit juice, Seville oranges (including any orange marmalade), or quinine (e.g., tonic water) from 48 hours (72 hours in the case of grapefruit juice and Seville oranges) before the first dose of study intervention until the last dose of study intervention.
- 2. Participants may not consume food containing poppy seeds from 72 hours before to completion of the screening visit.

#### 5.3.2. Caffeine, Alcohol, and Tobacco

- 1. Participants should abstain from using excessive alcohol or any illegal drugs within 3 days prior to Day 1 and at any time during the study. Current low to moderate use of alcohol as approved by the investigator may be continued unchanged.
- 2. The participant will be advised not to change the current use of caffeine and current smoking behavior.

# 5.3.3. Activity

- 1. Should avoid driving or operating complex machinery until the participant knows whether the drug adversely affects reaction time or impairs judgment.
- 2. Participants must avoid donating blood for at least 90 days after completion (i.e., final follow-up visit) of the study.

#### 5.4. Screen Failuresa

### Participant Identification, Enrollment, and Screening Logs

The investigator agrees to complete a participant identification and enrollment log to permit easy identification of each participant during and after the study. This document will be reviewed by the sponsor study-site contact for completeness.

The participant identification and enrollment log will be treated as confidential and will be filed by the investigator in the study file. To ensure participant confidentiality, no copy will be made. All reports and communications relating to the study will identify participants by participant identification and age at initial informed consent. In cases where the participant is not randomized into the study, the date seen and age at initial informed consent will be used.

Exceptional and limited re-testing of abnormal screening values, including laboratory values, that lead to exclusion are allowed only once to reassess eligibility. However, if the participant is a screen failure based on the adjudication process by independent experts from the epilepsy consortium at screening, re-testing will not be allowed.

\_

<sup>a This section has been amended by Amendment INT-1 and INT-3

If the adjudication process is not possible e.g., because of technical limitations of protected data transfer, the participant will not be a screen failure.

Individuals who do not meet the criteria for participation in this study (screen failure) may be rescreened one time after discussion with the sponsor representative. Rescreened participants will be assigned a new participant number, undergo the informed consent process, and then start a new screening and baseline phases. Rescreened individuals must meet all criteria before entering the double-blind phase.

[figure not shown]
#### 6. STUDY INTERVENTIONS

For description of the study intervention in the OLE period, see Section 10.6.

## 6.1. Study interventions Administereda

JNJ-40411813 will be supplied for this study as 25-mg and 50-mg tablets. Placebo will be supplied as matching tablets.

The tablets will be taken **CCI** from Day 1 to Day 85 (or day of Visit 7 when before Day 85). All study intervention, apart from the study intervention taken in the clinic during Visits 2, 4, and 6 will be taken at home and intake of the intervention should be confirmed in the e-diary.

The actual dose and the composition of tablets to be taken will be determined for each cohort and stratum within a cohort. In Table 1 below the most likely examples are presented. However, these examples may change based on actual dose decisions.

<sup>a This section has been amended by Amendment INT-1

A description of the study interventions is presented in Table 2:

**Table 2:** Description of Interventions

Table 2. Description of filter venti	0115	
Arm Name	JNJ-40411813	Placebo
Intervention Name	JNJ-40411813	Placebo
Type	Drug	Drug
Dose Formulation	Tablet	Tablet
Unit Dose Strength(s)	25 or 50 mg JNJ-40411813	Placebo
CCI		
Route of Administration	oral	oral
Use	experimental	Placebo-comparator
Investigational Medicinal Product (IMP) and Non-Investigational Medicinal Product (NIMP)	IMP	IMP
Sourcing	Provided centrally by the Sponsor	Provided centrally by the Sponsor
Packaging and Labeling	Provided in child-resistant packaging, labeled to meet applicable regulatory requirements.	Provided in child-resistant packaging, labeled to meet applicable regulatory requirements.
CCI		

## 6.2. Preparation, Handling, and Storage

All study intervention will be manufactured and provided under the responsibility of the sponsor. All study intervention will be provided in child-resistant high-density polyethylene bottles. All study intervention will be stored in a secure area with restricted access. Tablets must be stored at controlled room temperatures as indicated on the product specific labeling.

The investigator is responsible for ensuring that all study intervention received at the site is inventoried and accounted for throughout the study. The dispensing of study intervention to the

participant, and the return of study intervention from the participant, must be documented in the interactive web response system (IWRS) system. Participants must be instructed to return all original study intervention kits, whether empty or containing study intervention.

Study intervention must be handled in strict accordance with the protocol and the label. Unused study intervention, and study intervention returned by the participant, must be available for verification by the sponsor's study site monitor during on-site monitoring visits. The return to the sponsor of unused study intervention, or used returned study intervention for destruction, will be documented on the study intervention return form. When the study site is an authorized destruction unit and study intervention supplies are destroyed on-site, this must also be documented on the medication return form.

Study intervention should be dispensed under the supervision of the investigator or a qualified member of the study-site personnel, or by a hospital/clinic pharmacist. Study intervention will be supplied only to participants participating in the study. Returned study intervention must not be dispensed again, even to the same participant. Study intervention may not be relabeled or reassigned for use by other participants. The investigator agrees neither to dispense the study intervention from, nor store it at, any site other than the study sites agreed upon with the sponsor.

# 6.3. Measures to Minimize Bias: Randomization and Blindinga

#### **Procedures for Randomization**

Central randomization will be implemented in this study. Participants will be randomly assigned to one of two treatment groups based on computer-generated randomization schedules prepared before the study by, or under the supervision of the sponsor.

The randomization will be balanced by using randomly permuted blocks CCI

The IWRS will assign a unique treatment code, which will dictate the treatment assignment and matching study drug kits for the participant. The requestor must use his or her own user identification and personal identification number each time when contacting the IWRS and will then give the relevant participant details to uniquely identify the participant.

For programming of the IWRS-system, the following cohort numbers will be applied:

- Cohort 1: first cohort with **ECI** dose level (approximately 40 participants receiving JNJ-40411813 and approximately 20 receiving placebo)
- Cohort 2: second cohort with a dose level of (approximately 40 participants receiving JNJ-40411813 and approximately 10 receiving placebo)
- Cohort 3: third cohort with a higher dose if the efficacy of the higher dose used in Cohort 2 is still insufficient (approximately 40 JNJ/ approximately 10 placebo)

-

<sup>a This section has been amended by Amendment INT-1

• Cohort 4: this cohort includes both a lower dose and a higher dose. This cohort will randomize 100 subjects in a ratio 40:40:20 (high dose/low dose/placebo). This cohort may follow Cohort 2.

## **Blinding**

Blinded treatment will be used to reduce potential bias during data collection and evaluation of clinical endpoints. Participants and investigators will be blinded for treatment (JNJ-40411813 or placebo) but not for dose.

The investigator will not be provided with randomization codes. The codes will be maintained within the IWRS, which has the functionality to allow the investigator to break the blind for an individual participant.

Data that may potentially unblind the treatment assignment (e.g., study intervention plasma concentrations, plasma biomarkers) will be handled with special care to ensure that the integrity of the blind is maintained and the potential for bias is minimized. This can include making special provisions, such as segregating the data in question from view by the investigators, clinical team, or others as appropriate until the time of database lock and unblinding. Also, the site staff should not discuss insights on unblinding of randomization with the participants.

Under normal circumstances, the blind should not be broken until all participants have completed the study and the database is finalized. The investigator may in an emergency determine the identity of the treatment by contacting the IWRS. While the responsibility to break the treatment code in emergency situations resides solely with the investigator, it is recommended that the investigator contact the sponsor or its designee, if possible, to discuss the particular situation before breaking the blind. Telephone contact with the sponsor or its designee will be available 24 hours per day, 7 days per week. In the event the blind is broken, the sponsor must be informed as soon as possible. The date, time, and reason for the unblinding must be documented in the appropriate section of the electronic case report form (eCRF), and in the source document. The documentation received from the IWRS indicating the code break must be retained with the participant's source documents in a secure manner. Participants who have had their treatment assignment unblinded should continue to return for required follow-up evaluations.

In general, randomization codes will be disclosed fully only if the study is completed and the clinical database is closed. However, for the interim review in each cohort (see Section 9.5) and for unblinded review by the data review committee (DRC, see Section 7.1), the randomization codes and the translation of randomization codes into treatment and control groups will be disclosed to those authorized and only for those participants included in the interim review.

## 6.4. Study Intervention Compliancea

Study intervention will be taken by the participant at home or during a study visit in the clinic. The first dose will be taken by the participant at Visit 2 (Day 1) of the study in the clinic. The participant will be instructed to take their study intervention to the clinic at each study visit.

When in the clinic during visits 2 and 4, study intervention will be self-administered on site as outlined in Section 6.1. The administration of study intervention will be witnessed by the investigator or a properly trained designee. The exact date and time of study intervention administration will be recorded in the eCRF.

The participant will receive an e-diary to record – apart from seizures – the intake of the study intervention.

For study visits 2, 4 and 6, participants are requested to record the time of last dosing of levetiracetam or brivaracetam, their column and the study drug on the day before the study visit. Participants will also record the time of last dosing of levetiracetam or brivaracetam and study drug taken at home prior to visit 7. An appointment-card will be provided for documentation.

The investigator or designated study personnel will maintain a log in IWRS of all study intervention dispensed and returned. Study intervention supplies will be inventoried and accounted for throughout the study.

If appropriate, additional details may be provided in a pharmacy manual/study site investigational product manual that is provided separately and noted in Section 8.1, Study-Specific Materials.

# 6.5. Concomitant Therapyb

All prestudy therapies administered up to 30 days before screening must be recorded at screening (and confirmed by treating physician).

During the 8-week prospective pretreatment baseline period and during the 12-week double-blind treatment period, participants will continue to take their prescribed AEDs (one of which must include levetiracetam or brivaracetam) without change in dosage(s); new concomitant AEDs should not be added. For the concomitant AEDs including levetiracetam or brivaracetam, all doses within the limits of current clinical practice will be allowed. Concomitant AEDs will not be provided by the study sponsor.

Two exceptions to this rule will be allowed:

<sup>a This section has been amended by Amendment INT-1

[figure not shown]
b This section has been amended by Amendment INT-1

- Based upon clinical judgment, a one-time dosage adjustment of concomitant AEDs is permitted to mitigate adverse events attributable to those AEDs. Collection of blood for plasma concentration of these AEDs is allowed, at the discretion of the investigator.
- One-time changes in AED dosages do not represent a change in the daily AED regimen. For example, if the participant took an extra dose of an AED on one day, this would not represent a change in the daily AED regimen.

Rescue medication may be used as needed (PRN). Each administration of rescue medication must be documented in the seizure e-diary. However, benzodiazepines or barbiturates received on a continuing basis at stable dosages for 1 month before screening should be considered as concomitant AEDs. Benzodiazepines or barbiturates used as sleep aid or to treat anxiety will be allowed but should be documented in the eCRF.

For levetiracetam or brivaracetam drug intake on the days of study visits, the same rule applies as for JNJ-40411813: On the day of Visits 2, 4, 6 and 7 CCI will be taken in the study center during the study visit and CCI. Dosing during the site visit will be witnessed by the study staff. CCI. Participants taking levetiracetam XR should preferably take their medication in the morning and take this medication in the clinic during Visits 2, 4, 6 and 7. If the participant takes levetiracetam XR in the evening, this should not be changed for the study.

For study visits 2, 4, 6 and 7 participants are requested to record the time of last dosing of levetiracetam on the day before the study visit. Participants will also record the time that levetiracetam is taken at home prior to visit 7. An appointment-card will be provided for documentation.

Section 11.5 includes examples of disallowed CYP3A4 inhibitors (prohibited from 14 days or at least 5 times the drug's half-life, whichever is longer prior to study drug administration until the follow-up visit) and inducers (prohibited from at least 1 month prior to study drug administration until the follow-up visit).

Similarly, participants should avoid consumption of grapefruit, grapefruit juice and Seville oranges (including orange marmalade) and herbal products containing St. John's wort, ephedra, ginkgo, ginseng, or kava.

JNJ-40411813 itself is also an inhibitor of CYP3A4 and CCI or CYP3A4 metabolism and have a narrow therapeutic index with caution.

Examples of drug classes that include sensitive substrates to CYP3A4 and have a narrow therapeutic index include opioid analgesics, chemotherapy/oncologic agents, and immunosuppressive agents. Additional sensitive substrates that have a narrow therapeutic index include amiodarone, clindamycin, dihydroergotamine, dofetilide, ergotamine, and theophylline.

See Section 11.5 for an overview of drugs to be avoided.

If the administration of any concomitant therapy becomes necessary, it must be reported in the appropriate section of the eCRF.

The sponsor must be notified in advance (or as soon as possible thereafter) of any instances in which prohibited therapies are administered.

## 6.6. Recording of drug intake; overview

The participant will receive an e-diary to record the intake of the study intervention. In the e-diary, only confirmation of intake of study medication and rescue medication are recorded. The time of intake will not be recorded in the e-diary. Intake of rescue medication should also be recorded in the e-CRF.

For reasons of proper PK analysis of study medication, levetiracetam or brivaracetam and currently used AEDs that are substrate of CYP3A4, at some occasions the date and time of the drug intake needs to be recorded by the participant (using the subject participation card) or the investigator/site staff (using the eCRF) outside the scope of the e-diary.

An overview of this specific recordings of date and time of intake of AEDs is given in Table 3.

Study visit	When to record.	Study drug	Levetiracetam/ brivaracetam	CCI
2	Day before	Not applicable	By participant	By participant
Δ	During visit	By investigator	By investigator	By investigator
4	Day before	By participant	By participant	By participant
	During visit	By investigator	By investigator	By investigator
6	Day before	By participant	By participant	By participant
	During visit	By investigator	By investigator	By investigator
7	Same day, prior to the visit	By participant	By participant	Not applicable
	During visit	Not applicable	Not applicable	Not applicable

Table 3: Recording of date and time of last drug intake outside the scope of the e-diary.

# 6.7. Intervention After the End of the Studya

Investigators may re-contact the participant to obtain follow-up information regarding the participants' safety if there are any safety concerns at the last study visit.

Participants should continue taking the AEDs they were using during the study until such time as changes in their treatment are recommended by their treating physician. Changes in their treatment for epilepsy will be allowed when required during the follow-up period.

The sponsor has added an OLE period to this study (to be initiated when all required supplies are available), with eligibility for all participants who completed the double-blind study period and experienced no safety concerns.

<sup>a This section has been amended by Amendment INT-2

# 7. DISCONTINUATION OF STUDY INTERVENTION AND PARTICIPANT DISCONTINUATION/WITHDRAWAL

If a participant discontinues study intervention or withdraws from the study before the end of the double-blind period, the early withdrawal assessments (Visit 7) should be obtained.

# 7.1. Safety Data Review

Continuous or periodic blinded safety reviews will be done by the SRP. An unblinded review of the data (on the individual participant level) will be conducted if there are safety concerns from this blinded review as a result of severe, serious or unexpected AEs that are at least possibly related to the study intervention or if the frequency of discontinuations due to TEAEs exceeds 10% of the participants (see Section 7.4).

This unblinded review will be done by a DRC. A DRC will consist of at least one medical expert in the relevant therapeutic area and at least one statistician; committee membership responsibilities, authorities, and procedures will be documented in a separate charter.

In addition to the above, an interim unblinded review of safety, PK and efficacy data will be performed by an internal unblinded review committee as described in Section 9.5.

# 7.2. Completion

A participant will be considered to have completed the double-blind period of the study if he or she has completed the double-blind period up to Week 12 or has elected to exit after reaching the baseline monthly seizure count by Day 28 or exceeding the monthly baseline seizure count during a moving 28-day interval after Day 28. Participants who prematurely discontinue the study intervention for any other reason before completion of the double-blind period will not be considered to have completed double-blind period of the study.

Any participant who discontinues the study before Week 12 after receiving the study intervention will have an early withdrawal evaluation as described in Section 8.2.4.

Participants who discontinued the double-blind period for reason other than safety concerns, are allowed to enter the open-label extension period. See Section 10.

Participants who prematurely discontinue the study will not be replaced.

# 7.3. Participant Discontinuation/Withdrawal from the Studya

A participant will be withdrawn from the study for any of the following reasons. The participant must discontinue the study intervention and, whenever possible, the early withdrawal visit must be completed.

Lost to follow-up

-

<sup>a This section has been amended by Amendment INT-2

- Death
- Withdrawal of consent. When a participant withdraws consent, effort should be made to determine if the cause of withdrawal was due to tolerability or lack of efficacy.
- Noncompliance to take the study intervention. Noncompliance will be decided on a case-by-case basis depending on the number of missed tablets and the interval between missed doses.
- Experiences a severe adverse event or serious adverse event (SAE) while receiving treatment, that is considered at least possibly related to study drug.
- The investigator or sponsor believes (e.g., that for safety or tolerability reasons such as a SAE at least possibly related to the study intervention) it is in the best interest of the participant to discontinue the study intervention.
- A participant who shows signals of clinically meaningful acute suicidal ideation at any time during the study should be withdrawn from the study and promptly referred for appropriate medical/psychiatric care.
- The participant becomes pregnant.
- If the QTcF interval is higher than 500 msec or is prolonged >60 msec from the baseline (Screening) value. If the QTcF is not readily available, the QTcB may be used instead. The participant will continue to be monitored (maximum 12 hours) by repeated 12-lead ECGs (at least every 60 minutes) until the ECG normalizes.
- If the liver function tests exceed the values as presented in Section 11.7.

When a participant withdraws before completing the study, the reason for withdrawal is to be documented in the eCRF and in the source document. Study intervention assigned to the withdrawn participant may not be assigned to another participant.

# 7.4. Protocol Stopping Criteria

Blinded medical monitoring by the sponsor will occur on a continuous basis including AEs, laboratory and ECG data. When there is any concern about the safety of the participants as a result of severe or serious AEs that are at least possibly related to JNJ-40411813 or if the frequency of discontinuations due to TEAEs exceeds 10% of participants, an unblinded review of the safety data will take place (see Section 7.1). The cohort will be stopped at any time if significant safety concerns are related to JNJ-40411813 as per the reviewers' decision. However, if the safety observations allow, a new cohort with a lower dose of JNJ-40411813 may be started. If safety concerns continue, or when safety concerns are not expected to be solved by a dose reduction, the study will be stopped. The principal investigator (PI) may decide to stop study participation at any time when he/she estimates there is an acute risk for participants in study.

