# 4.2. Scientific Rationale for Study Design

# Design aspects and placebo control

A 1 to 3-cohort approach has been chosen to limit the number of participants exposed to study intervention and study procedures. Starting in Cohort 1 with a dose that is well tolerated but also expected to generate clinical effect, a rational decision may be taken based on ongoing assessment of the tolerability and safety whether in successive cohorts a higher or lower dose is needed for

optimal treatment. This decision may be based on the incidence of serious adverse events, or adverse events leading to discontinuation, as a cohort approaches full enrollment. Given a low incidence of these events, decision to evaluate of a higher dosage in the following cohort can be made, without pausing screening and enrollment.

The placebo response in studies in epilepsy may be significant (Goldenholz 2016). A placebo control will be used to establish the change in seizure count and the change in safety endpoints that may occur in the absence of active treatment.

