# Stratification JNJ-40411813 is metabolized mainly by CYP3A4. CCI

# **Optional dosage reduction**

As noted in the Investigator's brochure, dizziness, vertigo, coordination abnormal and fatigue are adverse drug reactions attributable to JNJ-40411813. Somnolence has also been reported. These are adverse events commonly seen with other AEDs; their frequency and severity may be related to dose and may be mitigated by temporary dose reduction or dose titration. Accordingly, if these adverse events occur with increasing frequency when dosages exceed ccl e.g. Cohort 2 and beyond, the investigator will have the option to reduce dosage temporarily, followed by rechallenge. The PI is encouraged to rechallenge the initial dose within 2 weeks if the Aes are resolved on the lower dose. If rechallenge is unsuccessful, i.e., the AEs recurred when the dose was increased, the dose may be reduced again and kept at that level.

This option will minimize the likelihood of dropout because of adverse events, and will provide experience to guide dosing instructions in future studies

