- For participants who entered open-label treatment phase ≥ 6 days from last dose of double-blind study intervention: open-label phase start date \leq AE onset date \leq date of the last dose of study intervention in the open-label phase plus 5 days.

Follow-up phase:

AEs that are assigned to the follow-up phase are not considered as treatment-emergent. AEs with onset date > date of last dose of double-blind study intervention plus 5 days will be assigned to this phase.

Summary tables will be provided for treatment-emergent adverse events:

- AEs
- Serious AEs (SAEs)
- AEs leading to discontinuation of each study drug within a study intervention/termination of study participation
- AEs by relationship to study intervention
- AEs leading to dose interruption of each study agent within a study intervention.

In addition to the summary tables, listings will be provided for participants who:

- Had SAEs
- Had AEs leading to discontinuation of study intervention/termination of study participation A listing of participants who died will be provided.

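### From Cohort 2 on, non-severe expected AEs managed by dose reduction count neither toward the 10% discontinuation trigger nor among the events named for moving to a higher dose without a pause

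*Protocol*

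**What the plan says.** **Review trigger.** Protocol 7.1 and 7.4 start an unblinded review by either of two routes. One is concern over particular events: 7.4 names "severe or serious AEs that are at least possibly related to JNJ-40411813", and 7.1 names "severe, serious or unexpected AEs that are at least possibly related to the study intervention". The other is numeric. In 7.1 it applies "if the frequency of discontinuations due to TEAEs exceeds 10% of the participants", and 7.4 repeats it: "if the frequency of discontinuations due to TEAEs exceeds 10% of participants, an unblinded review of the safety data will take place".

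**Next-cohort decision.** Protocol 4.2 (Design aspects and placebo control) says of the choice of a higher or lower dose: "This decision may be based on the incidence of serious adverse events, or adverse events leading to discontinuation, as a cohort approaches full enrollment". If those events are few, a higher dose may follow without a pause in screening or enrolment.

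**Dose reduction.** Protocol 4.2 (Optional dosage reduction) lets the investigator reduce the dose for dizziness-type events, fatigue and the like at dosages above a redacted level, giving Cohort 2 and beyond as the example. Rechallenge is encouraged, but after a failed rechallenge the participant may stay on the lower dose. The stated purpose is: "This option will minimize the likelihood of dropout because of adverse events". The risk table in 2.3.1 gives the same purpose.

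**Withdrawal.** Protocol 7.3 requires withdrawal of a participant who "Experiences a severe adverse event or serious adverse event (SAE) while receiving treatment, that is considered at least possibly related to study drug".

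**Reporting.** SAP 5.6.2 plans TEAE tables for AEs leading to discontinuation and for "AEs leading to dose interruption of each study agent within a study intervention". It has none for AEs leading to dose reduction. SAP 5.6.1 gives dose adjustments, with reasons, as a by-participant listing.

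**The concern.** The numeric trigger uses AE discontinuations as its measure of intolerance, and dose reduction exists to lower that measure. A participant who cannot tolerate the assigned dose because of non-severe dizziness or sedation, and who stays in the study on a lower dose, adds nothing to the 10% fraction. Nor does that participant add to the two event types that 4.2 names.

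The amendment history explains how this arose. The superseded Amendment 3 text required discontinuation if the events recurred after return to the assigned dose, so that participant would have been counted. The current text allows the participant to stay on the reduced dose, and the passages on the trigger and the next-cohort decision still name discontinuations only.

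Two things are at stake. The decision to open a higher-dose cohort could be made under the blind on a count that looks low partly because reductions replaced discontinuations. The final AE tables could also understate intolerance at the assigned dose. That would weaken one of the option's own stated aims in 4.2, to inform dosing in later studies.

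**Working it through.** The documents give no operating characteristic for the 10% trigger, so there is no planned figure to reproduce. The calculation shows only how sensitive the rule is to what it counts.

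**Inputs from the documents.** Cohort 2 has about 40 active and 10 placebo participants (Protocol 6.3). The threshold is more than 10% of participants, with no separate active-arm denominator.

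**Assumptions, not in the documents.** The 10% is read per cohort. A share p of active participants cannot tolerate the assigned dose. A share r of those is kept in the study on a reduced dose, and the rest discontinue. No AE discontinuations occur on placebo unless stated.

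**Step 1: threshold.** 10% of 50 is 5, so more than 10% needs at least 6. With none on placebo, that is 6/40 = 15% of the active arm. As an arithmetic extreme, 5 of 40 could discontinue and the other 35 (35/40 = 87.5%) be dose-reduced for non-severe events. The fraction would be 5/50 = 10%, which does not exceed 10%.

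**Step 2: one look at 50 participants.** P(X ≥ 6), where X ~ Binomial(40, p(1 − r)). For p = 0.20 and r = 0.5 the rate is 0.20 × 0.5 = 0.10, and P = 0.21.

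| p | r = 0 | r = 0.5 | r = 0.75 |
|---|---|---|---|
| 0.15 | 0.57 | 0.08 | <0.01 |
| 0.20 | 0.84 | 0.21 | 0.01 |
| 0.25 | 0.96 | 0.38 | 0.04 |

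**Step 3: placebo discontinuations.** With p = 0.20 and r = 0.5, adding Binomial(10, 0.02) or Binomial(10, 0.05) placebo discontinuations raises 0.21 to 0.24 or 0.29.

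**Step 4: continuous monitoring.** Protocol 7.4 describes continuous blinded monitoring, so a single look at 50 may understate the chance of crossing. I simulated the running fraction for p = 0.20. It was checked after each participant from number 10 or number 30 up to 50, assuming that outcomes are known in enrolment order.

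| r | one look at 50 | from participant 30 | from participant 10 |
|---|---|---|---|
| 0 | 0.84 | 0.94 | 0.96 |
| 0.5 | 0.21 | 0.43 | 0.59 |
| 0.75 | 0.01 | 0.08 | 0.21 |

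Continuous checking softens the loss but does not remove it.

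**Step 5: which events fall in the gap.** Related severe or serious events lead to withdrawal under 7.3 and are in the event route of the trigger; 7.1 adds unexpected ones. What remains is non-severe and expected. Amendment 4's summary describes the target events as dizziness, incoordination, sedation or fatigue that may limit daily activities. That can fit the moderate grade in Protocol 11.4, which is interference with normal activity.

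**The case against.** There is a substantial case on the other side, and most of it narrows the point.

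- **Second route to review.** Concern over severe, serious or unexpected related AEs prompts review with no minimum count. This stands. A reader might infer that any poorly tolerated dose can pass both rules; the documents do not support that, because the gap is limited to non-severe, expected events.
- **Permissive wording.** Protocol 4.2 says that the decision may rest on the named events, and the sentence before it refers to ongoing assessment of tolerability and safety. The sponsor is free to look at dose reductions. Nothing requires it, and a low count of the two named events is the stated ground for not pausing.
- **Limited reach.** The option is tied to dosages above a redacted level, with Cohort 2 and beyond as the example. On that text the Cohort 1 trigger and the opening of Cohort 2 are not affected.
- **Backstop.** Protocol 9.5 requires an unblinded review of all cumulative safety data once at least 45 Cohort 2 participants have completed 4 weeks. This is real protection, but the no-pause decision can come first.
- **Unseen criteria.** The charters (7.1, 9.5) and the separate short SAP for the two review committees (SAP 5.8.1) were not available. They may already include dose reductions.
- **7.3 and 4.2.** A reader might infer a flat contradiction for severe related events. Withdrawal in 7.3 is mandatory and reduction in 4.2 is optional, so both can be followed, and redaction may hide a severity limit. What remains is a need for clarification.
- **Comparator.** A reader might take 0.84 as the position before Amendment 4. It is not: Amendment 3 already allowed a temporary reduction, and participants who tolerated the return to full dose were not counted.
- **Reporting.** With about 40 active participants per cohort, reductions could be counted by hand from the listing. That is true, but it leaves a tolerability rate by arm to the reader's own tally.

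**Conclusion.** The point holds in limited form. From Cohort 2 on, non-severe expected AEs managed by dose reduction are outside the discontinuation route of the trigger and outside the events that 4.2 names, although reduction is meant to replace discontinuation and may be permanent. The SAP tabulates discontinuation and interruption but not reduction.

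With 20% intolerance among 40 active participants and half kept on a reduced dose, the chance of crossing 10% is 0.21 instead of 0.84 at a single look. It is 0.43 to 0.59 instead of about 0.94 to 0.96 under continuous checking from participant 30 or 10. These figures rest on assumed rates, a per-cohort reading of the 10% and no placebo discontinuations. They show direction and rough size, not the trial's actual risk.

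A reader might infer that every reduction should simply be added to the same 10%. The documents do not settle that. In the single-look example it would raise the chance of triggering from 0.21 to 0.84, and it would treat a brief reduction with successful rechallenge like a discontinuation. That is a safety rule for the sponsor to decide.

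**What to change.** 1. In SAP 5.6.2, add a TEAE table of AEs leading to dose reduction, and a combined row for discontinuation or dose reduction, by arm and cohort.
2. In the ongoing safety review (7.1, 7.4) and the next-cohort decision (4.2), review the pooled blinded count of AE dose reductions alongside AE discontinuations. Show separately the participants not returned to the assigned dose.
3. The sponsor should reconcile 7.1, 7.4 and the next-cohort text of 4.2 with the dose-reduction provision, and clarify how 7.3 and 4.2 apply to severe related AEs. If the charters or the committees' SAP already cover dose reductions, a cross-reference would do for the monitoring part. No threshold or clinical rule is proposed here.

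The cost is some protocol and SAP wording, one more table and somewhat more monitoring work. Dose adjustments and their reasons are already planned for listing under SAP 5.6.1, so no new data collection should be needed.
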